### **6.3. Carfilzomib Dose Modifications for Non-Hematologic Toxicities**

Treatment with carfilzomib and panobinostat should be held for  $\geq$  grade 3 events until resolved to  $\leq$  grade 1 or return to baseline. If the adverse event was not treatment-related, or was attributable to panobinostat, subsequent treatment with carfilzomib may be resumed at full dose after resolution to  $\leq$  grade 1 or return to baseline.

If the event was carfilzomib-related, subsequent treatment with carfilzomib will resume at one level dose reduction (see Table 3). If toxicity continues or recurs, a 2nd carfilzomib dose reduction is permitted unless the patient is already receiving the lowest dose level shown in Table 3. If toxicity continues, the patient should be discontinued from treatment.

If there is no resolution of carfilzomib-related toxicity after 2 weeks of withholding carfilzomib (up to 3 weeks for infection treatment), carfilzomib will be discontinued.

Specific carfilzomib-associated non-hematologic toxicities are addressed in Table 7.

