## **6. DOSE MODIFICATIONS**

The criteria for interruption and resumption of treatment due to toxicity are outlined in the following tables. Dose re-escalation will not be allowed in any patient. All toxicities will be graded utilizing the NCI CTCAE v4.0. If toxicity occurs, the toxicity will be graded, and appropriate supportive care treatment will be administered to decrease the signs and symptoms thereof. If one drug is held, treatment may continue with the other study drug as appropriate. If study medication is held for over 3 weeks due to toxicity, that study medication will be discontinued. Treatment medications will be adjusted with a one level dose-reduction. The dose level criteria in Table 3 should be used to adjust the panobinostat or carfilzomib dose in the event of toxicity. If patients who are on the lowest allowable dose have a toxicity requiring dose reduction, the offending agent should be discontinued. Either or both drugs may be adjusted according to the dose modification tables below.

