**Table 7: Criteria for Dose Reductions, Delays and/or Re-Institution Due to Drug-Related QTcF Abnormalities**

ECG TIME POINT	ABNORMALITY	DOSE MODIFICATION GUIDELINE
Dose modifications are based on local readings of the average QTcF of triplicate ECGs.		
Cycle 1 Dose Modification Criteria:		
Cycle 1 PRE-DOSE Days 1 and 5 Triplicate ECGs	Day 1: Average QTcF: >450 msec	Check and correct the patient's serum potassium, magnesium, calcium, phosphorus immediately, as well as evaluate concomitant medications. If abnormality noted on Cycle 1 Day 1: Repeat 3 pre-dose ECGs. If the 3 pre-ECGs: Do not meet criteria again, discontinue patient from study. Do meet criteria for dosing; administer panobinostat.
	Day 5: Average QTcF: ≥480 msec to <500 msec Or >60 msec increase from baseline average	If abnormality noted on Cycle 1 Day 5: Delay dose at least 3 days and repeat 3 pre-dose ECGs. If the repeat 3 pre-dose ECGs: Do not meet pre-dose ECG criteria again, discontinue panobinostat. Do meet pre-dose ECG criteria for dosing and QTc prolongation determined to be related to panobinostat, resume panobinostat treatment with a 1-level dose reduction. If however, it was determined that the QTc prolongation was secondary to electrolyte abnormalities or concomitant medications, continue at the same dose level. Repeat ECGs – pre-dose (x3), 3-hours post-dose (x3), on the next scheduled dosing day.
	Average QTcF: ≥500 msec	Check and correct the patient's serum potassium, magnesium, calcium and phosphorus immediately. Discontinue patient from panobinostat.  If however, it was determined that the QTc prolongation was secondary to electrolyte abnormalities or concomitant medications: Omit dose. On the next scheduled dosing day continue at the same dose level. Repeat ECGs - pre-dose (x3), 3-hours post-dose (x3), on the next scheduled dosing day.

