**Table 8 Carfilzomib Dose Modifications for Non-Hematologic Toxicity**

Event	Action to be Taken
Hypertensive crisis, or Pulmonary hypertension, or Pulmonary toxicity	Stop carfilzomib until resolved or returned to baseline. Consider whether to restart carfilzomib based on a benefit/risk assessment.
Other non-hematologic toxicity assessed as carfilzomib-related $\geq$ Grade 3	Hold dose until toxicity resolves to $\leq$ Grade 1 or baseline. Restart at 1 dose decrement.

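### Section 6.3 and the dose-modification tables give incompatible instructions for a few grade 3 or higher non-hematologic events, and no text says which prevails

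*Combined protocol and SAP*

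**What the plan says.** **Section 6.3, general rule.** "Treatment with carfilzomib and panobinostat should be held for" grade 3 or higher events until grade 1 or baseline. Attribution is not a condition of the hold; it only sets the restart dose. If the event was unrelated to treatment or "was attributable to panobinostat, subsequent treatment with carfilzomib may be resumed at full dose" once it has resolved. By contrast: "If the event was carfilzomib-related, subsequent treatment with carfilzomib will resume at one level dose reduction". Carfilzomib is discontinued if related toxicity has not resolved after 2 weeks of withholding (up to 3 weeks for infection treatment).

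**Section 6.3, link to the specific rows.** "Specific carfilzomib-associated non-hematologic toxicities are addressed in Table 7". Table 7 is headed "Criteria for Dose Reductions, Delays and/or Re-Institution Due to Drug-Related QTcF Abnormalities"; the carfilzomib table is Table 8.

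**Table 8.** Grade 3 neuropathy: keep dosing, hold only after more than two weeks, release at grade 2 or lower without pain, restart one decrement lower. Grade 2-3 hypersensitivity: hold to grade 1, restart at full dose. Grade 3-4 infection: hold until systemic treatment is complete, restart at full dose if there is no neutropenia. The catch-all row covers other grade 3 or higher "toxicity assessed as carfilzomib-related".

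**Table 6 (panobinostat).** Grade 4 fatigue: interrupt to grade 2 or baseline, then restart, at an unchanged dose if resolved within 7 days. A note to the same table says patients with a grade 4 event should be discontinued from study drug.

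**Section 6.** "If one drug is held, treatment may continue with the other study drug as appropriate". Also: "Dose re-escalation will not be allowed in any patient".

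**The concern.** A dose-modification section has to give one answer for each event. Here a site that applies Section 6.3 literally and a site that applies the table row can both say they followed the protocol, yet treat the same grade 3 event differently. One withholds carfilzomib and the other gives it, or one restarts at full dose and the other a level lower. Because re-escalation is not allowed, a lower restart dose lasts for the rest of treatment.

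The trial is multicenter, and Section 10.5 makes tolerability of the combination the primary safety endpoint. Dose holds, reductions and repeat toxicity after restart all bear on that endpoint. If they depend partly on which paragraph a site reads, the tolerability data are harder to interpret, and the patient's dose after a serious toxicity is left to chance.

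**Working it through.** The plan gives no figure to reproduce. The check sets the texts side by side and sizes the differences from the dosing tables.

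**1. Grade 3 neuropathy**

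| | Section 6.3 | Table 8 |
|---|---|---|
| At onset | Hold both drugs | Continue carfilzomib |
| Release | Grade 1 or baseline | Grade 2 or lower without pain |
| Not resolved at two weeks | Discontinue carfilzomib if related | Hold begins; restart possible one level lower |

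The first and third rows cannot both be followed. The release thresholds coincide for a patient who entered with painless grade 2 neuropathy and differ for those who entered lower.

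Carfilzomib is given on days 1, 2, 8, 9, 15 and 16 of 28. Counting doses in a 14-day window from each onset day 1 to 28 gives a minimum of 2 (for example, days 17-30 contain next-cycle days 1 and 2) and a maximum of 4 (days 1-14 contain 1, 2, 8 and 9). The mean is 6 × 14 / 28 = 3.0. For neuropathy lasting through the window, Table 8 therefore allows 2 to 4 doses where Section 6.3 allows none.

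On frequency, Section 1.3.1 reports single-agent grade 3/4 neuropathy of 2.2% and 0.7%. If those rates carried over to the combination, which is an assumption, that would be 80 × 0.022 = 1.76 and 80 × 0.007 = 0.56 patients. The rates include grade 4, which is not in dispute.

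**2. Carfilzomib-related grade 3 hypersensitivity, or grade 3-4 infection without neutropenia**

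Table 8 restarts at full dose; Section 6.3 restarts one level down. The Table 4 steps are 56, 45 and 36 mg/m2, with six doses per cycle from Cycle 2.

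| Dose level | Table 8 restart | Section 6.3 restart | Per cycle | Difference |
|---|---|---|---|---|
| 4 | 45 | 36 | 45 × 6 = 270 vs 36 × 6 = 216 | 54 / 270 = 20.0% |
| 5 and 6 | 56 | 45 | 56 × 6 = 336 vs 45 × 6 = 270 | 66 / 336 = 19.6% |

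This assumes no earlier reduction and onset after the 20 mg/m2 doses on Cycle 1 Days 1-2. It is one protocol dose step, carried through every later cycle. The documents give no rate of either event for the combination.

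**3. Grade 4 fatigue**

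This conflict lies inside Table 6: the row restarts panobinostat, the note discontinues. No arithmetic applies.

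**4. Does any text settle precedence?**

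The last sentence of Section 6.3 is the only link from its general rule to the carfilzomib rows. It says the specific toxicities are dealt with elsewhere, cites Table 7, and does not say the rows override the rule. Section 6 says either or both drugs may be adjusted by the tables, again without ranking them against Section 6.3. Neither sentence can resolve item 3.

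**The case against.** The best reply is that specific rules override general ones and that the protocol signals this. Table 8 follows Section 6.3 directly and almost shares its title. The wrong number is one of several off-by-one pointers: dose steps cite Table 3 for Table 4, neutropenia cites Table 4 for Table 5, and QTc management cites Table 6 for Table 7. No site would look for neuropathy in a QTcF table. Section 6.3's 3-week allowance for infection matches Table 8's infection row, so the two were meant to be read together. Most of this stands: the rows were very probably intended as exceptions. But probable intent is not a stated rule, and it leaves the fatigue contradiction untouched.

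A reader might infer wider conflict. The documents do not support it:

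- **Catch-all row.** It is silent on events not related to carfilzomib; it does not tell sites to continue. Section 6.3 already holds both drugs for them. The only pull the other way is Section 6's permissive sentence about continuing the other drug.
- **Heart failure.** Section 6.3 says carfilzomib may resume at full dose if the event was unrelated, so a reduced dose satisfies both texts.
- **Renal.** The trigger is creatinine clearance, not grade, and the restart is one decrement, as in Section 6.3 for related events.
- **Tumor lysis and herpes.** These rows are not graded, so a conflict needs an added assumption about grade.
- **Grade 4 and laboratory discontinuations.** Stopping permanently does not breach a hold, and Section 6.3 sets no panobinostat restart dose to contradict.

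**Conclusion.** The point holds for three items: grade 3 neuropathy; the restart dose after carfilzomib-related grade 3 hypersensitivity or non-neutropenic grade 3-4 infection; and grade 4 fatigue within Table 6. The restart-dose difference is one level, about 20% of the per-cycle carfilzomib dose, for a patient not previously reduced. The neuropathy difference is 2 to 4 doses over two weeks, and possibly discontinuation against a later restart.

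The number of patients is likely small and cannot be quantified from the documents. Single-agent neuropathy rates suggest one or two at most for that item, if they apply. Phase I patients with a Cycle 1 DLT are outside the point, because Section 5.2.2 already holds treatment for them.

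A reader might go on to infer a bias in the response rate or a problem with the sample size. Nothing in the documents supports either. The consequence is inconsistent toxicity management and less interpretable tolerability data, which is worth correcting but does not undermine the design.

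**What to change.** - **Section 6.3.** Change the closing pointer from Table 7 to Table 8 and add: *This hold rule is the default; event-specific rows in Tables 6 and 8 take precedence where they differ.*
- **Section 6.** To the sentence letting the other drug continue, add: *except where Section 6.3 holds both drugs.* Section 6.3's existing hold then governs unlisted events whatever the attribution.
- **Table 6.** Either except fatigue from the grade 4 discontinuation note or change the fatigue row to discontinue.

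The cost is amendment wording only: no added patients, visits or procedures. The changes keep the rules the protocol already contains. Table 8's full-dose restarts and its two-week neuropathy window would become explicit exceptions, and carfilzomib would still be withheld for unlisted grade 3 or higher events it did not cause, as Section 6.3 already requires.

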**Table 8. Carfilzomib Dose Modifications for Non-Hematologic Toxicity**

Event	Action to be Taken
Allergic reaction/hypersensitivity Grade 2 – 3 Grade 4	Hold until ≤ Grade 1, reinstitute at full dose. Discontinue
Tumor lysis syndrome  (≥ 3 of following: ≥ 50% increase in creatinine, uric acid, or phosphate; ≥ 30% increase in potassium; ≥ 20% decrease in calcium; or ≥ 2-fold increase in LDH)	Hold carfilzomib until all abnormalities in serum chemistries have resolved. Reinstitute at full doses.
Infection Grade 3 or 4	Hold carfilzomib (no more than 3 weeks) until systemic treatment for infection complete. If no neutropenia, restart at full dose. If neutropenic, follow neutropenic instructions (Table 4).
Herpes zoster or simplex of any grade	Hold carfilzomib until lesions are dry. Reinstitute at full dose.
Neuropathy Grade 2 treatment emergent neuropathy with pain or Grade 3 neuropathy  Grade 4 neuropathy	Continue to dose. If neuropathy persists for more than two weeks hold carfilzomib until resolved to ≤ Grade 2 without pain. Then restart at 1 dose decrement  Discontinue carfilzomib
Renal Dysfunction  CrCl ≤ 30 mL/min	Hold until CrCl > 30 mL/minute; restart at 1 dose decrement
Congestive heart failure	Any subject with symptomatic congestive heart failure, whether or not drug related, must have the dose held until resolution or return to baseline, after which treatment may continue at a reduced dose, or the subject may be withdrawn from the study. If no resolution after 2 weeks, the subject will be withdrawn from the study.
Hypertension	All patients should be evaluated for hypertension and treated as needed. If hypertension cannot be controlled, reduce carfilzomib.

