## 5. STUDY DESIGN

This is an open-label, non-randomized Phase I/II study of patients with relapsed or refractory multiple myeloma.

The Phase I study will determine the MTD of the combination of carfilzomib and panobinostat. The Phase I portion will follow a standard dose escalation design, beginning with dose level 1 (see Table 2). Patients will be assessed for dose-limiting toxicity (DLT) at each visit during Cycle 1 prior to receiving treatment. Dose modifications will not be permitted during Cycle 1 unless a patient experiences a DLT (see Section 5.2.2.). Treatment cycles will be administered at 28-day intervals. Panobinostat will be administered orally three times weekly during weeks 1 and 3 of each cycle (Days 1, 3, 5, 15, 17, 19). Carfilzomib will be administered intravenously on Days 1, 2, 8, 9, 15, and 16 of each cycle. During Cycle 1, the carfilzomib dose will be escalated after the Day 2 dose, if well tolerated.

A maximum of four dose levels were evaluated. No DLTs were seen during the Phase I portion.

In the Phase II portion of this study, patients with relapsed/refractory multiple myeloma will receive treatment with the dose level 4 panobinostat and carfilzomib combination. Patients will be reevaluated for response to treatment after each cycle (4 weeks). Patients with objective response or stable disease will continue treatment, with subsequent reevaluations every 4 weeks, until disease progression or unacceptable toxicity occurs.

[figure not shown]
A parallel Phase I study will occur to evaluate a minimum of 3 patients and a maximum of 6 patients following a standard dose escalation design at additional dose levels of the combination of carfilzomib and panobinostat (see Table 3).

If additional dose levels are found to be tolerable, then additional patients will be recruited into an expansion cohort which will be open at all sites - a maximum total of 36 patients (including the ones recruited into the parallel Phase I study) will be treated at this dose level. Sites will be notified about the expansion cohort and patients will enter in the dose level confirmed in their enrollment confirmation from SCRI Innovations.

Up to 80 eligible patients will be treated in the Phase I/II study. The treatment schema for the study is shown in Figure 2.

Figure 2

Treatment Schema

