**Table 3. Parallel Dose Escalation Study – Dose Levels 5 and 6**

28-Day Cycles	Cycle 1	Cycle 2 to Progression
Dose Level 5		
Carfilzomib	20 mg/m  IV D 1, 2 / 56 mg/m  IV D 8, 9, 15, 16	56 mg/m  IV D 1, 2, 8, 9, 15, 16
Panobinostat	30 mg D 1, 3, 5, 15, 17, 19	30 mg D 1, 3, 5, 15, 17, 19
Dose Level 6		
Carfilzomib	20 mg/m  IV D 1, 2 / 56 mg/m  IV D 8, 9, 15, 16	56 mg/m  IV D 1, 2, 8, 9, 15, 16
Panobinostat	20 mg D 1, 3, 5, 15, 17, 19	20 mg D 1, 3, 5, 15, 17, 19

A parallel Phase I study will occur to evaluate a minimum of 3 patients and a maximum of 6 patients following a standard dose escalation design at additional dose levels of the combination of carfilzomib and panobinostat.

Patients will enter in the dose level confirmed in their enrollment confirmation from SCRI Innovations.

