### 5.2.2. Definitions of Dose-Limiting Toxicity (DLT)

For the purpose of determining the MTD (see Section 5.2.3), DLT is defined as any of the following that are determined to be related to study treatment during **Cycle 1**:

- Grade 4 neutropenia (absolute neutrophil count [ANC] <500/ $\mu$ L) for >7 days.
- Febrile neutropenia (ANC <1000/ $\mu$ L with fever >101°F [38.5°C]).
- Grade 3 thrombocytopenia with  $\geq$  Grade 2 bleeding.
- Grade 4 thrombocytopenia (platelets <25,000/ $\mu$ L) > 7 days (patients may receive platelet support/transfusion).
- $\geq$  Grade 2 neuropathy with uncontrolled pain
- $\geq$  Grade 3 non-hematologic drug-related toxicity (excluding alopecia) despite optimal supportive care lasting >72 hours or requiring a dose reduction in the first cycle.
- Patients who are unable to receive 75% of the required doses of both agents secondary to toxicity.

Adverse events will be graded using the National Cancer Institute (NCI) Common Toxicity Terminology Criteria for Adverse Events v4.0 (CTCAE v4.0).

Dose modifications are not permitted during Cycle 1 in any cohort unless the subject experiences a DLT. Subjects in dose level -1 (see Table 2) who develop a DLT during Cycle 1 will be discontinued from the study. Subjects in dose level 1 or higher who experience a DLT during Cycle 1 will have treatment held. The DLT will be counted toward the assessment of the MTD for the given cohort; however, the subject may continue on therapy if the toxicity resolves and dose modifications can be implemented according to the dose modification guidelines in Section 6.0.

Patients who withdraw from the study before receiving 75% of their scheduled Cycle 1 doses due a non-drug related AE (i.e., tumor progression) will be considered inevaluable and will be replaced.

Patients without clinical evidence of progressive disease at the end of the first cycle of study therapy will continue treatment. Patients will be reevaluated for response after completing 2 cycles (8 weeks) of treatment. Patients with objective response or stable disease according the International Myeloma Working Group Uniform Response Criteria (see Appendix C) will continue treatment, with reevaluations until disease progression occurs, unacceptable toxicity develops, or the subject chooses to discontinue study treatment.

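### Table 8 tells sites to keep giving carfilzomib for painful Grade 2 or Grade 3 neuropathy, with no exception for a Cycle 1 DLT that Section 5.2.2 says must be held

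*Combined protocol and SAP*

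**What the plan says.** **Table 8, neuropathy row.** For treatment-emergent Grade 2 neuropathy with pain, or Grade 3 neuropathy: "Continue to dose. If neuropathy persists for more than two weeks hold carfilzomib". Carfilzomib then restarts one dose level lower, once the neuropathy is Grade 2 or less without pain. For Grade 4 the action is "Discontinue carfilzomib". The row is not limited to any cycle or phase.

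**Section 5.2.2.** Two criteria can make treatment-related Cycle 1 neuropathy a DLT:
- severity at or above "Grade 2 neuropathy with uncontrolled pain";
- Grade 3 or worse, if it outlasts 72 hours of optimal support or forces a dose reduction.

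The action is "Subjects in dose level 1 or higher who experience a DLT during Cycle 1 will have treatment held". After that, the subject "may continue on therapy if the toxicity resolves and dose modifications can be implemented according to the dose modification guidelines in Section 6.0".

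**Section 5.** "Patients will be assessed for dose-limiting toxicity (DLT) at each visit during Cycle 1 prior to receiving treatment".

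**Section 6.3, lead text.** "Treatment with carfilzomib and panobinostat should be held for" events of Grade 3 or worse, until they return to Grade 1 or baseline. The section then refers the reader to Table 7 for specific carfilzomib toxicities, but Table 7 covers QTcF. The intended table is Table 8.

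**Section 5.2, Table 3.** For dose levels 5 and 6: "A parallel Phase I study will occur to evaluate a minimum of 3 patients and a maximum of 6 patients". Section 5 reports that dose levels 1 to 4 were evaluated without a DLT.

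**The concern.** Uncontrolled pain is a form of pain, so a Grade 2 or Grade 3 neuropathy DLT in Cycle 1 also falls in the Table 8 row. One section then says hold and the other says continue for up to two weeks. No sentence says which takes precedence.

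The risk is practical. A site finds a neuropathy DLT at the pre-dose check, looks up the action in the dose-modification table, and is told to give the next infusion. At levels 5 and 6 that infusion can be 56 mg/m², the highest carfilzomib dose in the study.

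For Grade 3 neuropathy the conflict is wider. Table 8 also disagrees with the lead text of its own section, in every cycle and in Phase II.

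**Working it through.** The plan gives no figure to reproduce. The check compares the instructions and then counts the infusions at issue.

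**Step 1. Where the rules collide**

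| Neuropathy (treatment-related, Phase I Cycle 1) | DLT under 5.2.2? | 6.3 lead text | Table 8 |
|---|---|---|---|
| Grade 2, pain controlled | No | Silent (starts at Grade 3) | Continue |
| Grade 2, pain uncontrolled | Yes, at onset: hold | Silent | Continue |
| Grade 3, pain controlled, gone within 72 hours, no dose reduction | No | Hold both drugs | Continue |
| Grade 3, pain uncontrolled | Yes, at onset: hold | Hold both drugs | Continue |
| Grade 3, beyond 72 hours despite support, or needing a reduction | Yes: hold | Hold both drugs | Continue |
| Grade 4 | Yes, if a criterion above is met: hold | Hold both drugs | Discontinue carfilzomib |

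The first row shows no conflict. For Grade 2 with uncontrolled pain, Section 5.2.2 is the only hold: the 6.3 lead text and the catch-all rows of Tables 6 and 8 all start at Grade 3. For Grade 3, Table 8 conflicts with 6.3 whether or not the event is a DLT, and this continues after Cycle 1 and into Phase II.

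**Step 2. Infusions inside the two-week window**

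Inputs, from Table 3: Cycle 1 carfilzomib at levels 5 and 6 is 20 mg/m² on Days 1 and 2, then 56 mg/m² on Days 8, 9, 15 and 16. Let d be the onset day, counted after any dose that day.
- DLT met at onset (uncontrolled pain): count infusion days after d, up to d + 14.
- DLT met only after 72 hours (Grade 3): count infusion days after d + 3, up to d + 14.

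| Onset day | DLT at onset | mg/m² | DLT after 72 hours | mg/m² |
|---|---|---|---|---|
| 1 | 1 × 20 + 3 × 56 | 188 | 3 × 56 | 168 |
| 2–4 | 4 × 56 | 224 | 4 × 56 | 224 |
| 5 | 4 × 56 | 224 | 3 × 56 | 168 |
| 6–7 | 4 × 56 | 224 | 2 × 56 | 112 |
| 8 | 3 × 56 | 168 | 2 × 56 | 112 |
| 9–11 | 2 × 56 | 112 | 2 × 56 | 112 |
| 12 | 2 × 56 | 112 | 1 × 56 | 56 |
| 13–14 | 2 × 56 | 112 | 0 | 0 |
| 15 | 1 × 56 | 56 | 0 | 0 |
| 16 on | 0 | 0 | 0 | 0 |

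For onset on Day 2 or later, the window covers every remaining Cycle 1 infusion, so Table 8 alone would never stop one.

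**Step 3. Patients who could be affected**

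If the limit of 3 to 6 patients applies to each level, 2 × 3 to 2 × 6 gives 6 to 12. If it covers both levels together, 3 to 6. These are patients at risk, not expected events.

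The protocol gives no Cycle 1 rate for painful Grade 2 or for Grade 3 neuropathy. Section 1.3.1 reports Grade 3/4 neuropathy of 2.2% at 20 mg/m² and 0.7% on the 20/27 mg/m² schedule. Purely as an assumption, applying these to 6 to 12 patients gives 6 × 0.007 = 0.04 to 12 × 0.022 = 0.26 events. Those rates cover more than Cycle 1, which makes them too high here. They also come from lower carfilzomib doses without panobinostat and omit painful Grade 2, which makes them too low.

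**The case against.** The strongest reply is that the protocol already settles the matter. An event becomes a DLT only through Section 5.2.2, which itself says to hold, wait for resolution and then go to Section 6. Section 5 requires the DLT check before each Cycle 1 treatment. To go wrong, a site must recognise the DLT, ignore the action stated beside the definition, and dose from a general table. For Grade 3 it must also ignore the text introducing that table. This largely stands, and it is why the point is minor. It does not remove the contradiction, because no sentence gives the order of precedence, and Grade 2 with uncontrolled pain has no second safeguard.

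Some stronger readings are tempting, but the documents do not support them:
- *That the plan intends dosing through neuropathy DLTs.* Sections 5 and 5.2.2 point the other way.
- *That four extra infusions are to be expected.* Four is a ceiling. It needs early onset (Days 2 to 7, or Days 2 to 4 if the DLT is met only after 72 hours) and a missed hold at each later visit.
- *That levels 5 and 6 are known to be open.* The text is in the future tense, but those levels came in with Amendments 3 and 4 in 2013 and the latest amendment is from August 2015. The documents do not say whether enrollment had finished.
- *That the neuropathy row must be an error because it alone says to continue.* Of the ten event types in Table 8, eight hold, stop or discontinue in at least their listed cases, and hypertension is treated and then reduced. Toxicities may properly be managed differently, so this count proves nothing.
- *That MTD determination is affected.* The DLT counts toward the MTD whichever action follows. The DLT definition, the escalation rule and the Phase II sample size are unchanged.

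**Conclusion.** The contradiction is in the current text. Table 8 conflicts with Section 5.2.2 for Phase I Cycle 1 neuropathy DLTs of Grade 2 or 3. For Grade 3 in any cycle or phase it also conflicts with the lead text of Section 6.3.

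The likely reach is small. The Cycle 1 conflict concerns at most 6 to 12 patients at levels 5 and 6 (3 to 6 if the cohort limit is joint), and only if those cohorts are still enrolling. The worst case per patient is four further infusions, 224 mg/m², and it assumes that a site follows Table 8 alone. No event count can be estimated from the documents.

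This is a minor safety-wording correction with no effect on the statistical design. A reader might infer that Table 8, as the more specific text, should override the Grade 3 hold. Nothing in the protocol says so, and it would be the less protective choice.

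**What to change.** Add to the Table 8 neuropathy row: *Exception: in Phase I Cycle 1, neuropathy meeting a Section 5.2.2 DLT criterion: hold treatment per 5.2.2; once resolved, restart carfilzomib at 1 dose decrement (Grade 4: discontinue carfilzomib).*

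Correct the Section 6.3 pointer from Table 7 to Table 8. Ask the sponsor to state which rule governs Grade 3 neuropathy outside Cycle 1 DLTs.

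Two additions should be avoided:
- A sentence making Table 8 rows override the Grade 3 hold. It would also remove the hold at onset for Grade 3 hypertension, whose row says only to treat and then reduce.
- A new recovery threshold. The neuropathy row already has one. A stricter one, combined with the Section 6.3 rule that stops carfilzomib when related toxicity has not resolved after two weeks of withholding, could turn held doses into permanent discontinuation.

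The cost is wording in an amendment. Some carfilzomib doses will be held, as Section 5.2.2 already requires, and a patient whose neuropathy is slow to resolve could reach the two-week limit and lose the drug.

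### Grade 3–4 symptomatic heart failure has inconsistent stopping and restart rules across Table 8, Section 6.3 and Section 6.4.1, and Section 6.3 points to the wrong table

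*Combined protocol and SAP*

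**What the plan says.** Five places in the combined protocol and SAP bear on Grade 3–4 symptomatic heart failure.

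- **Table 8, congestive heart failure row.** "Any subject with symptomatic congestive heart failure, whether or not drug related, must have the dose held until resolution or return to baseline". What comes next is either a lower dose or exit: "after which treatment may continue at a reduced dose, or the subject may be withdrawn from the study". The row then sets a limit: "If no resolution after 2 weeks, the subject will be withdrawn from the study".
- **Section 6.3, first paragraph.** Both drugs are held for Grade 3 or higher events. "If the adverse event was not treatment-related, or was attributable to panobinostat, subsequent treatment with carfilzomib may be resumed at full dose" once the event has settled.
- **Section 6.3, third paragraph.** The rule is that when "there is no resolution of carfilzomib-related toxicity after 2 weeks of withholding carfilzomib (up to 3 weeks for infection treatment), carfilzomib will be discontinued". Panobinostat and study participation are not mentioned.
- **Section 6.4.1.** It names congestive heart failure among the cardiac events seen with carfilzomib and notes that deaths have occurred. For Grade 3–4 cardiac events it keeps carfilzomib off until the patient recovers, and then asks the site to weigh a restart one level lower. It gives no time limit and does not mention Table 8.
- **Section 6.** Any study drug held for toxicity for more than 3 weeks is stopped.

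Section 6.3 closes with "Specific carfilzomib-associated non-hematologic toxicities are addressed in Table 7". Table 7 is headed "Criteria for Dose Reductions, Delays and/or Re-Institution Due to Drug-Related QTcF Abnormalities"; the carfilzomib table is Table 8. Section 8.2.6 refers the reader to 6.3, 6.4 and the Investigator's Brochure without ranking them.

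**The concern.** A site treating one such patient can find three different instructions for day 14: withdraw the patient, stop carfilzomib only, or keep holding with restart still open. If the event is judged unrelated or due to panobinostat, it can also find two different restart doses. A site working from 6.4.1 alone could re-expose a patient whom Table 8 and the third paragraph of 6.3 would not. A site working from the first paragraph of 6.3 could give full dose where Table 8 requires a lower one. The protocol itself records fatal outcomes for this type of event. The stake is patient safety and consistency between sites, not the primary analysis.

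**Working it through.** The plan states no figure to reproduce. The check sets the rules side by side and then sizes the gaps.

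**1. The rules compared**

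| Provision | Events covered | Unresolved at 2 weeks | Restart dose after resolution |
|---|---|---|---|
| Table 8, heart failure row | Symptomatic, any grade, any cause | Subject leaves the study | Reduced dose, or withdrawal |
| 6.3, first paragraph | Grade 3 or higher, unrelated or due to panobinostat | No 2-week rule | Full dose allowed |
| 6.3, second and third paragraphs | Carfilzomib-related | Carfilzomib stopped | One level lower |
| 6.4.1 | Grade 3–4 cardiac, under a heading for carfilzomib-related events | Still held, restart open | One level lower, if restarted |
| Section 6 | Any hold for toxicity | Hold may run to 3 weeks | One level lower |

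**2. Carfilzomib-related event**

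If it resolves within 2 weeks, all the applicable rules are compatible: a reduced dose, with withdrawal as an option under Table 8. If it does not, Table 8 and the third paragraph of 6.3 both end carfilzomib. They differ on whether the patient also leaves the study. Only 6.4.1, read by itself, leaves carfilzomib restart open.

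**3. Event not attributed to carfilzomib**

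The third paragraph of 6.3 does not apply by its own wording, and 6.4.1 sits under a heading for carfilzomib-related events. The conflict is between the first paragraph of 6.3 (full dose, no 2-week limit) and Table 8 (reduced dose or withdrawal, with a 2-week limit).

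**4. Length of the window**

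The 2-week limit is 14 days and the Section 6 ceiling is 21 days: 21 − 14 = 7 days, that is days 15–21. This takes the Section 6 ceiling to cover the hold whatever the attribution.

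**5. Size of the dose gap**

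Inputs: full doses from Table 2 (dose level 4, 45 mg/m²) and Table 3 (dose levels 5 and 6, 56 mg/m²), and the Table 4 steps 15, 20, 27, 36, 45, 56 mg/m². Table 8 does not say how far to reduce. One level is assumed, following the general rule in Section 6, with no previous reduction.

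- Dose level 4: 45 / 36 = 1.25, so full dose is 25% higher. Over the six infusions of a cycle from Cycle 2: 6 × 45 = 270 against 6 × 36 = 216 mg/m².
- Dose levels 5 and 6: 56 / 45 = 1.244, so 24% higher. Per cycle: 6 × 56 = 336 against 6 × 45 = 270 mg/m².

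These are dose ratios, not estimates of added cardiac risk.

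**The case against.** The strongest reply is that the rules can all be obeyed together. Withdrawing the subject at 2 weeks also discontinues carfilzomib. Section 6.4.1 only asks the site to consider a restart; it neither requires one nor expressly allows a hold beyond 2 weeks. The Table 8 row is mandatory, specific to the event and indifferent to attribution, while full-dose resumption in 6.3 is only permitted. Section 8.2.6 sends the reader to both 6.3 and 6.4, so reading 6.4.1 in isolation is itself a mistake. The pointer error belongs to a general slip of one in the table numbers: Section 6 cites Table 3 for the dose steps in Table 4, and the Table 8 infection row cites Table 4 for Table 5. Table 8 follows directly after the faulty sentence.

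Much of this stands. A careful reader would apply Table 8, and the hold is not open-ended because Section 6 caps it at 3 weeks. What remains is that 6.4.1 is also specific to cardiac events, no text ranks the provisions, and the sentence that should lead to the controlling row names the QTcF table. Full dose and reduced dose cannot both be right for the same patient.

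A reader might also infer a further contradiction from the second paragraph of 6.3. After a second reduction it says "If toxicity continues, the patient should be discontinued from treatment", while Section 6 stops only the drug responsible. The documents do not support this as a general conflict. The Section 6 sentence concerns patients already on the lowest allowable dose, which is 15 mg/m² in Table 4. Two reductions lead to 27 mg/m² from 45 (45, 36, 27) and to 36 mg/m² from 56 (56, 45, 36). Among dose levels 1 to 6, only level 1 (27, 20, 15) reaches it. The wording there may be a deliberate choice by the sponsor.

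**Conclusion.** The inconsistency is real but narrow. It concerns Grade 3–4 symptomatic heart failure in two situations: not resolved after 2 weeks of holding, or not attributed to carfilzomib and ready for restart. For a carfilzomib-related event, restart after day 14 arises only if 6.4.1 is read alone. For other events it also arises under the first paragraph of 6.3. The exposure at issue is a 7-day window and one dose step (25% or 24% higher at full dose), given the assumptions of a single-level reduction and a 3-week ceiling that covers the hold.

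Few patients are likely to be affected. This is a judgement: at most 80 patients are treated, and entry requires a normal ejection fraction and excludes NYHA class III–IV failure. The documents give no carfilzomib heart-failure rate and no time to resolution from which a number could be derived.

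A reader might infer that the protocol sets no limit on the hold, or that the trial's efficacy conclusions are affected. Neither is supported: Section 6 sets a ceiling, and sample size, alpha and power do not depend on these rules. The correction is worth making because the rules govern dosing after an event with reported deaths and can be reconciled at almost no cost.

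**What to change.** - **Section 6.4.1.** Add: *Symptomatic congestive heart failure follows the Table 8 row, whether or not drug related: if unresolved after 2 weeks, carfilzomib is not restarted and the subject is withdrawn from the study.*
- **Section 6.3, last sentence.** Change the reference from Table 7 to Table 8 and add: *Where a Table 8 row states a different action or time limit, that action or limit applies; otherwise the 6.3 rules, including the 2-week limit, still apply.* The second clause matters. A blanket override by Table 8 would remove the 2-week stop from rows with no limit of their own, such as tumor lysis syndrome, renal dysfunction, pulmonary hypertension and the row for other non-hematologic toxicity.
- **Section 6.3, first paragraph.** In the sentence on full-dose resumption add: *except symptomatic congestive heart failure (see Table 8)*.
- **Section 6.** State that shorter hold limits in 6.3 and Table 8 take precedence over the 3-week ceiling.

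Cost: one sentence each in 6.4.1 and Section 6, and in 6.3 a corrected number, one sentence and one clause. No procedures, visits or patients are added.
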